Many practitioners also use fillers with high G prime along the jawline or lateral face to accomplish improving the jowls. This technique, alternatively called "jawline filler, jawline lift", has not received FDA approval. JUVÉDERM VOLUMA® XC injectable gel is currently FDA approved for deep injection in the cheek area to correct age-related volume loss. In practice, we have seen the advent of cheek treatments with Voluma causing noticeable lifting in the jowls and also the nasolabial fold. However, recent experimentation with filler into the mandible lateral to the jowl, sometimes accompanied by injection into the preauricular area by this author has revealed that this area has been underrepresented in filler solutions for jowling.

Protocol Summary

This study is proposed to evaluate the best protocol for achieving improvement in the sagging jawline.

JUVÉDERM VOLUMA™ XC will be injected in each of 16 women with sagging of grades 1-3 using a published jawline evaluation scale (1).

Patients will be randomized 1:1 into 2 groups:

Patient Group 1: JUVÉDERM VOLUMA™ XC 1-2 syringes (each syringe is 1 cc) will be injected bilaterally into the lateral jawline and inferior cheek area (preauricular area) (the latter area will be added if necessary to achieve visual improvement in jowl attenuation). Total syringes used per person will have a range of 1-2)

Patient Group 2: JUVÉDERM VOLUMA™ XC 1-3 syringes (each syringe is 1 cc) will be injected bilaterally into the lateral cheek (zygomatic) area plus JUVÉDERM VOLUMA™ XC 1-2 syringes (each syringe is 1 cc) will be injected into the lateral jawline and inferior cheek area (preauricular area) (the latter area will be added if necessary to achieve visual improvement in jowl attenuation). Total syringes used per person will have a range of 2-5)

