- c. There may be discomfort / pain / bruising and complete discussion of side effects potentially resulting from the treatment, including possible stroke, blindness and scarring
- d. Transient edema may occur immediately following the treatment.
- e. Erythema and bruising may occur following treatment and last up two weeks or longer.
- f. A full disclosure and written consent will be provided and signed.
- g. If necessary as deemed by patient and/or physician, a touch up may be performed at the 1-month visit.
- h. Evaluations by phone and/or telemedicine will be performed at 72 hours after treatment, 6 and 12 months.
- I. Patients will complete a safety diary daily via email for 30 days following treatments.

If the patient passes all of the inclusion and exclusion criteria for entry into the study the investigator will obtain signed Informed consent, enroll the patient into the study, and record required data on the appropriate study data form. Pre-treatment photographs will be taken.

Treatment

- 1. Photographs will be taken prior to treatment with the VISIA CR system and Fotofinder and with an iPad. Frontal, 45- and 90-degree angle shots at standard illuminations will be taken.
- 2. Patients will be randomized to 2 groups:

Patient Group 1: JUVÉDERM VOLUMA™ XC 1-2 syringes (each syringe is 1 cc) in will be injected bilaterally into the lateral Jawline/lateral medial or and inferior cheek area (preauricular area) (the latter area will be added if necessary to achieve visual improvement in jowl attenuation). Total syringes used per person will have a range of 1-2.

Patient Group 2: JUVÉDERM VOLUMA™ XC 1-3 syringes (each syringe is 1 cc) will be injected bilaterally into the lateral cheek (zygomatic) area plus JUVÉDERM VOLUMA™ XC 1-2 syringes (each syringe is 1 cc) will be injected into the lateral jawline and inferior cheek area (preauricular area) (the latter area will be added if necessary to achieve visual improvement in jowl attenuation). Total syringes used per person will have a range of 2-5.

Note: Based on preclinical studies and a toxicological risk assessment, subjects will be limited to 20 mL of JUVEDERM VOLUMA™XC per 60 kg (130 lbs) body mass per year. This includes any "Touch-up Volume"

3. During treatment cold air will be directed toward the injection sites to reduce discomfort.

- 4. Any complications will be noted at each visit and the patient will complete a diary via email or text every day.

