Photographs will remain unretouched. One blinded dermatologist and one unblinded dermatologist will rate the patient's severity of jowling based on the Jawline Rating Scale (JRS) (1) at baseline, the 4-week, 8-week, and 12 or 16-week visits. The patient will also rate their jowling based on the JRS as well as their satisfaction with the procedure.

Analysis of Scientific Soundness of the Protocol

The proposed study has been designed to provide a valid method to analyze the safety and efficacy of facial volume replacement. Measure taken to assure that the study provides valid data are as follows:

- 1. Photographs will be taken under standardized conditions. Photographs will be taken with a VISIA CR, a device made by Canfield Scientific specifically to be utilized for clinical research to provide uniformity in patient photographs.
- 2. Adverse or unanticipated effects that occur during the course of this clinical study will be recorded and carefully analyzed as to their relationship to the treatment.
- 3. Evaluators will review individual photos without knowledge of if they are before or after photos.

Primary Outcome Measure:

The primary outcome is a reduction of 1 or more points of the Jawline Rating Scale (JRS)
 Assessment (on scale of 0 to 4) at baseline versus that at 4 weeks from the last injection (whether initial or touch-up) based on any or all of one blinded dermatologist rating, one unblinded dermatologist rating, and patient rating. (A lower number will mean a better outcome) Time Frame: Baseline to 4 weeks after last injection.

Secondary Outcome Measures

- 1. Reduction of 1 or more points of the Jawline Rating Scale (JRS) Assessment (on scale of 0 to 4) at baseline versus that at 4 weeks from the last injection based on the patients rating while looking in the mirror and at before and after photographs. A lower number will mean a better outcome. Time Frame: 4 weeks from last injection
- 2. Whether group 1 and group 2 has a higher reduction in the Jawline Rating Scale (JRS) (on scale of 0 to 4) at 4 weeks from the lastinjection compared to baseline based on ratings from one blinded dermatologist and one unblinded dermatologist. A lower number will mean a better outcome. Time Frame: 4 weeks from last injection

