- 3. Whether group 1 or group 2 has a higher reduction in the Jawline Rating Scale (JRS) (on scale of 0 to 4) at 4 weeks from the last injection compared to baseline based on the patients rating while looking in the mirror and at before and after photographs. A lower number will mean a better outcome. Time Frame: 4 weeks from last injection
- 4. Jawline Rating Scale (JRS) Assessment on scale of 0 to 4 at 4 weeks: One blinded dermatologist and one unblinded dermatologist will rate the patient's severity of jowling based on the Jawline Rating Scale (JRS). The patient will also rate their jowling based on the Jawline Rating Scale (JRS). The scale is on a rating of 0 to 4. A lower number will mean a better outcome. [Time Frame: 4 weeks]
- 5. Jawline Rating Scale (JRS) Assessment on scale of 0 to 4 at 8 weeks: One blinded dermatologist and one unblinded dermatologist will rate the patient's severity of jowling based on the Jawline Rating Scale (JRS). The patient will also rate their jowling based on the Jawline Rating Scale (JRS). The scale is on a rating of 0 to 4. A lower number will mean a better outcome. [Time Frame: 8 weeks]
- 6. Jawline Rating Scale (JRS) Assessment on scale of 0 to 4 at 12 or 16 weeks: One blinded dermatologist and one unblinded dermatologist will rate the patient's severity of jowling based on the Jawline Rating Scale (JRS). The patient will also rate their jowling based on the Jawline Rating Scale (JRS). The scale is on a rating of 0 to 4. A lower number will mean a better outcome. [Time Frame: 3 months from last treatment]
- Incidence of abnormal eye exam (Confrontational Visual Fields Exam) findings (Safety):
 Ophthalmologic exams that include Confrontational Visual Fields Exam will be performed prior to any
 treatment, 30 minutes after treatment, and at all follow up in-person visits. [Time Frame: up to 18
 months]
- 8. Incidence of abnormal eye exam (Snellen Eye Exam) findings (Safety):
 Ophthalmologic exams that include Snellen Eye Exam will be performed prior to any treatment, 30 minutes after treatment, and at all follow up in-person visits. [Time Frame: up to 18 months]
- 9. Incidence of abnormal eye exam (Ocular Motility Exam) findings (Safety):
 Ophthalmologic exams that include Ocular Motility Exam will be performed prior to any treatment,
 30 minutes after treatment, and at all follow up in-person visits. [Time Frame: up to 18 months]

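### Masking of the blinded dermatologist to treatment arm is neither specified nor protected, although uncropped photographs may show the zygomatic cheek, which is injected only in Group 2

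*Combined protocol and SAP*

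**What the plan says.** **Treatments.** Under Protocol Summary and Treatment item 2, Group 2 has 1-3 syringes "injected bilaterally into the lateral cheek (zygomatic) area" in addition to the jawline treatment. Group 1 has no zygomatic injection. Both groups may have the inferior (preauricular) cheek injected if needed.

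**Images.** Treatment item 1: "Frontal, 45- and 90-degree angle shots at standard illuminations will be taken". Data Analysis: "Photographs will remain unretouched". Neither section mentions cropping or masking any part of the face.

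**Raters.** Data Analysis: "One blinded dermatologist and one unblinded dermatologist will rate the patient's severity of jowling based on the Jawline Rating Scale (JRS) (1) at baseline", and again at the follow-up visits.

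**Masking.** Analysis of Scientific Soundness of the Protocol, item 3: "Evaluators will review individual photos without knowledge of if they are before or after photos". This concerns time point. No section says that the blinded dermatologist is unaware of the arm, or how that would be kept.

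**Arm comparison.** Secondary outcome 2 compares the groups on reduction in the Jawline Rating Scale (JRS), "compared to baseline based on ratings from one blinded dermatologist and one unblinded dermatologist". Secondary outcome 3 makes the same comparison "compared to baseline based on the patients rating while looking in the mirror and at before and after photographs".

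**Blinded Physician Assessment form.** The rater first gives a JRS grade. A later item asks for a judgement of improvement from the pre-injection photograph and the current one. The text of this form is broken in extraction, but the two-part structure is legible.

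**The concern.** The two arms differ by volumising filler in a part of the face that the jawline scale does not grade but that a frontal or oblique photograph may show. The Study Rationale itself reports that cheek treatment visibly lifts the jowls and the nasolabial fold. A rater who sees the whole face, and who at each rating visit is also shown the pre-injection image beside the current one, may notice midface change and connect it with Group 2.

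What is at stake is Endpoint #2, the question of which method is superior. The ratings behind it come from an openly unblinded dermatologist, from patients who are not described as masked, and from the blinded dermatologist. The last is the only source that could be masked to arm. If that masking leaks, no masked evidence remains for the comparison, and later analysis cannot restore it.

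**Working it through.** The plan gives no figure on this point, and no alpha, power, effect size or SD, so there is nothing to reproduce. The check compares sections and then works out how sensitive the comparison is.

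**1. Is there a visual difference between arms outside the graded region?** Yes, at one site. The zygomatic cheek is treated only in Group 2. The preauricular cheek is optional in both groups and does not identify an arm.

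**2. Could the rater see it?** The listed views are frontal, 45 and 90 degrees, without retouching. The framing handed to the rater is not stated, so exposure of the midface is neither confirmed nor prevented.

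**3. Does the described masking cover it?** No. Item 3 of the soundness section hides whether an image is before or after. Hiding the time point does not hide the arm.

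**4. Does the rater see a paired comparison?** The form includes one, after the JRS grade. The same rater completes the form at successive visits, so what is seen in the pair at 4 weeks can carry into the JRS grade at 8 weeks and later. Within one visit, a grade given before the pair is less exposed. The paired item also sits uneasily with the time-point masking in item 3; that is a separate matter.

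**5. How is baseline rated?** In both Appendix 1 schedules, Blinded Evaluation is marked at screening but Photography is not; it starts at the treatment visit. A live baseline rating is therefore possible. It precedes treatment and cannot itself reveal the arm, but it would give the rater a full-face reference.

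**6. Which outcomes are exposed?** Secondary outcome 2 is. Secondary outcome 3 uses patients' ratings only. The primary outcome is a reduction of at least 1 point from baseline and does not compare arms.

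**7. Sensitivity.** Inputs: 16 patients (Scope) randomised 1:1 (Protocol Summary), so 16/2 = 8 per arm if balanced.
- Blinded rating alone, one patient shifted by one grade: 1/8 = 0.125 grade in the arm difference. Two patients: 2/8 = 0.25. Four patients: 4/8 = 0.5.
- Two dermatologists' ratings averaged (an assumption; the protocol does not say how they are combined), with only the blinded grade shifted: (1/2)/8 = 0.0625 grade per patient.

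**8. Illustration under assumptions not in the documents.** Take a two-sided alpha of 0.05, no true difference between arms, a bias b in the arm difference, and an SD of JRS change of 0.5, 0.75 or 1.0. Then SE = SD × √(2/8) = 0.5 × SD, and the false-positive rate is Φ(b/SE − 1.96) + Φ(−b/SE − 1.96).

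| Bias b | SD 0.5 | SD 0.75 | SD 1.0 |
|---|---|---|---|
| 0 | 5% | 5% | 5% |
| 0.25 | 17% | 10% | 8% |
| 0.5 | 52% | 27% | 17% |

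For example, b = 0.25 and SD = 0.5 give SE = 0.25, b/SE = 1, and Φ(−0.96) + Φ(−2.96) ≈ 0.17. This is a normal approximation applied to an ordinal scale with 8 per arm, so it is only a rough guide. It shows what bias of a given size would do, not that such bias occurs.

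**The case against.** A reader might infer that the blinded rater can tell the arms apart, so that the blind fails. The documents do not support that. They do not show that zygomatic filler is recognisable in a 4-week photograph, and the lift that the Study Rationale reports concerns the jowls and nasolabial fold, not cheek fullness. They list camera angles, not the images given to the rater. The JRS grade comes before the paired item on the form, and a single image offers no baseline for judging a cheek. It is also too broad to say that the cheek is injected only in Group 2, since the preauricular cheek is optional in both arms.

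Nor is a direction of bias supported. The Study Rationale reports benefit from cheek filler but goes on to say that the mandibular area has been neglected, and the Introduction leaves the comparison open. Nothing records what the blinded dermatologist expects. A size stated as responder percentage points would not fit either, because no arm comparison is defined on responders.

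Finally, the comparison is secondary, it already includes an unblinded rating, and cropping one rater's images does not mask the other.

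These objections limit the claim but do not remove the gap. The cue may be present, repeated paired viewing by the same rater makes it easier to notice, and no section guards against it. That the other ratings are unmasked makes this one more worth protecting. The protocol also accepts the principle: Exclusion Criteria item 10 bars lower-face features that could bias the assessment.

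**Conclusion.** Masking of the blinded dermatologist to treatment arm is neither specified nor protected, and midface change may reveal the arm. The frequency of recognition and the direction of any bias are unknown. The consequence is confined to the dermatologist-rated arm comparison (secondary outcome 2, Endpoint #2); the primary outcome is not affected as an arm comparison.

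The size is 0.125 grade in the blinded rater's arm difference for each patient graded one step differently, or 0.0625 if the two dermatologists' ratings are averaged. This rests on 8 patients per arm; the averaging is an assumption. The point is a cheap improvement worth making before any rating is done, not a demonstrated failure of the blind.

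**What to change.** In Data Analysis and the soundness section, state that:
- the blinded dermatologist is masked to treatment arm;
- this rater scores only photographs, for both the JRS grade and the improvement item, and the baseline grade comes from the pre-treatment photographs (the screening entry in Appendix 1 should be aligned);
- these images are cropped to the lower face, with one standard crop per view (frontal, 45 and 90 degrees) for all patients and visits, leaving out the zygomatic cheek and as much of the nasolabial fold as the view allows;
- full-face originals are kept. Cropping is not retouching, so the existing sentence can stand;
- the arm comparison from the blinded rating is reported separately from the unblinded rating.

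Cost: about 16 × 4 = 64 image sets to crop (baseline, 4, 8, and 12 or 16 weeks), and up to about 16 × 5 = 80 if every patient has a touch-up and the extra one-month visit described under Return Visits. No extra staff or patient visits are needed. The rater loses some midface context, and cues may remain if cheek filler also changes the lower face.

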While rare, unintentional injection into a blood vessel has been reported for facial injections which can be serious and may be permanent. Any incidence of visual disturbances (including, but not limited to, any loss of vision, blurry vision, double vision, pain in or around the eye, blind spot or shadow in the visual field, trouble

moving eyes, dizziness, confusion, weakness or numbness of the arms or legs, changes to consciousness or alertness, difficulty speaking or speech impairment, facial drooping etc.) will be immediately reported to the treating physician and the sponsor. In the event of blindness or any ophthalmic signs or symptoms, the subjects must undergo immediate evaluation by a retinal specialist. More details pertaining to the reporting protocol and treating vascular compromise will be outlined below.

The incidence of serious adverse events associated with intravascular injection is very low. If a complication occurs, the subject will be advised to contact the study staff and treating physician immediately and the treating physician will use his/her medical judgement to determine the necessary interventions to treat the subject.

There are also unforeseeable risks or results associated with this procedure. If the subject experiences any unanticipated adverse event an additional visit and/ or report form may be required.

Vascular Compromise Procedure and Protocol

Recognition and Treatment of Vascular Occlusion:

Recognition:

Recognize vascular occlusion by a livedoid or violaceous appearance to the treatment area and/or blanching of the treatment area and/or patient pain.

Early signs:

- Blanching followed by violaceous patches in distribution of artery
- Pair
- * especially if they have had a filler treatment before and it is unusual and/or more severe in days following injection

Delayed signs:

- Violaceous or dusky reticulated patches in distribution of arteries
- Pain
- Necrosis

Arterial Compromise vs. Bruising:

- Does not typically develop yellow coloration like bruising
- Not typically round or in dependent areas like bruising

Treatment:

When vascular occlusion is suspected, it is crucial that the injection is stopped immediately and treatment is rapidly instigated. The objective is to facilitate blood flow to the affected area. The steps for treatment of a vascular occlusion are:

- 1. Immediately flood the entire treatment area with injected 200-300 U of Hyaluronidase (1.25-2.0 cc of Hylenex, 150 u/cc).

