^{*} Safety Eye Assessments will be performed prior to treatment and 30 minutes after treatment

^{**}Patient diary to be completed daily by email for 30 days following treatment

^{***}No Retreatment done per patient and/or physician

advanced Jowl Improvement with Injectable Fillers: Jawline Injections alone vs Jawline and Cheek Injections

Blinded Physician Assessment

Patient Number	Date:			
Baseline or Date pos Baseline or Date Pos	t 1 st Injection: Baselin st 2 nd Injection: Baselin	e4w8w_ ne4w8w_	12 week 16 12 week 16	16 week sweek
No.	OMAZ -	- CMAZ	CMAZ	SMB2
OMerz O	- OMerz	CMerz CMerz	GMerz S	©Merz.
0	1	2	3	4
No sagging	Mild sagging	Moderate sagging	Severe sagging	Very severe sagging
pictured above, put a	etructions: Without reference X by the value you 3 4	feel represents the a		
the patient prior to in	jection and the photogoutting an X by the varied	graph of the patient to	oday, please evaluate	
Comments:				
Blinded Physician: Date:	Name	Sig	nature	

advanced Jowl Improvement with Injectable Fillers: Jawline Injections alone vs Jawline and Cheek Injections 10001

Subject Self-Assessment of Results

Patient Number				
Date:				
Baseline or Date post Or: Date Post 2 nd Injection	-	line 4 w 8 8w 12 w_		16 week
©Merz ©Merz	OMerz	SMerz	CMerz CMerz	CMerz CMerz
3	1	1	3	1
0	1	2	3	4
No sagging	Mild sagging	Moderate sagging	Severe sagging	Very severe sagging
Grading of Jowls Instructured above, put an				
1 2	34	_ 5		
Grading of Jowls by p yourself prior to inject putting an X by the va	ion and the photogra	ph of yourself today, p	olease evaluate your	
Much improved Improved No change Worse Much Worse	-			
Comments:				
Signature of Coordi	nator	Date:		

	Iowl/Jawline Study Iumber	10001-Patient Diary		Date
	e treatment			
many da	ys it has been since	= :	ne questions v	patient number, the date, and how which require to answer mild,
• N	Moderate: minimal,	and/or local or noninva out not immediately life	sive intervent	only; no intervention needed tion needed nospitalization or prolongation of
Have y	you experien	ced any of the fo	ollowing s	symptoms?
	oderate to Severe Di yes was it Mild	zziness Moderate		NO
	onfusion yes was it Mild	Moderate		NO
		s in your arms or legs Moderate		
	nanges to consciousn yes was it Mild	ess or alertness Moderate		NO
		eech impairment Moderate		
If		Moderate	Severe	
				bove questions, pleas
 1811 91 2 2 2 2 2 2 2 2 2 2 2 2 2 2 2 2 2 	L1 and seek i	mmediate medi	cal attent	ion.

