sp	ots, problems movin		YES	ain in or around your eye, blindness, NO
		any portion of the face? Moderate		
• Cr	rusty or scabby skin a	round the eyelids or any o		e face NO
Ify	es was it Mild	Moderate		

		in in any area?	YES	_ NO	_
	If yes was it Mild	Moderate	Severe		
•	Moderate to Severe He			NO	_
	If yes was it Mild	Moderate	Severe		
•	Fever			_ NO	_
	If yes was it Mild	Moderate	Severe		
•	Difficulty Chewing or Sv	vallowing	YES	NO	_
	If yes was it Mild	Moderate	Severe	.	
•	Moderate to Severe Pa	in in Jaw at Rest	YES	NO	
	If yes was it Mild				
*If	you have answ	ered yes to ar	ny of the abo	ve ques	tions, please c
ie d	office immedia	tely at [name] durin	g busine	ess hours, or D
	at [name]				-
и и к	[name]	do il alter liot	 		
	These questions will any of the following	•	vents that may occ	ur. Please le	et us know if you have
1.	Have you noticed an				NI -
	•	y other symptoms no	ot listed above?		
	If yes, list symptoms				
	If yes, list symptoms If yes was it Mild Have you had any co	Moderate_	Severe since your last diar	y? Yes	 No
2.	If yes, list symptoms If yes was it Mild Have you had any co If yes, please list Have any symptoms	Moderate_ ontinuing symptoms s	Severe since your last diar	y? Yes	No
2.	If yes, list symptoms If yes was it Mild Have you had any co If yes, please list Have any symptoms If yes, please list Any change in medic	Moderate_ ontinuing symptoms s /side effects subside	Severe since your last diar	y? Yes Yes	No
2.	If yes, list symptoms If yes was it Mild Have you had any co If yes, please list Have any symptoms If yes, please list Any change in medic Yes No	Moderate_ ontinuing symptoms s /side effects subside	Severe since your last diar diary?	y? Yes Yes lications sin	No No No ce your last visit or di
2.	If yes, list symptoms If yes was it Mild Have you had any co If yes, please list Have any symptoms If yes, please list Any change in medic Yes No If yes, list medication Have you been diagnorms	Moderate_ontinuing symptoms solutions symptoms solutions subside cations, including over the cations of t	Severe since your last diary? d since last diary? er the counter medical conditions	y? Yes Yes lications sin	No No ce your last visit or di

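### The daily diary asks about dizziness only when it is moderate or severe, although the protocol wants any dizziness reported immediately

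*Combined protocol and SAP*

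**What the plan says.** The rule is one sentence in the Adverse Reactions section. It opens with "Any incidence of visual disturbances (including, but not limited to, any loss of vision, blurry vision, double vision, pain in or around the eye", continues through "moving eyes, dizziness, confusion, weakness or numbness of the arms or legs, changes to consciousness or alertness", and closes with "difficulty speaking or speech impairment, facial drooping etc.) will be immediately reported to the treating physician and the sponsor". No item in it carries a minimum severity.

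The Safety Assessments section makes the daily diary the tool for monitoring adverse events. The Appendix 1 footnotes have it completed by email every day for 30 days after treatment.

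The first symptom block of the Patient Diary carries symptoms from that list and ends with an instruction to call 911. Its dizziness question survives in the extracted text as "oderate to Severe Di yes was it Mild", with the rest of the word dizziness on the next line. The question below it survives as "onfusion yes was it Mild". Both are followed by a mild, moderate or severe choice.

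**The concern.** The diary is the only safety instrument that reaches the patient every day, and its printed instruction is what tells her to act at once. The text available does not say how soon staff read the emailed entries, so a recorded answer cannot be assumed to produce immediate contact. If the form sets a higher threshold than the protocol's reporting rule, a patient who follows the form exactly can fail to trigger that rule.

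At stake is prompt notice of a possible early neurological symptom after filler injection. The sponsor already treats dizziness as an alarm symptom, since it stands in the 911 block. Adverse events are also a secondary outcome, so the wording influences which mild events the diary records. Sample size, power and error rates are not affected.

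**Working it through.** No arithmetic underlies this point. It is a comparison of texts.

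1. **Trigger in the protocol.** Adverse Reactions: any incidence, with dizziness named and not graded. Action: immediate report to the treating physician and the sponsor.
2. **Trigger in the diary.** First block, dizziness question: moderate or severe only. Action after a yes: call 911.
3. **Mild dizziness under each.** Under the protocol it is reportable at once. Under the diary the truthful answer to the question as worded is no, and the closing instruction, which applies to a yes, does not apply.
4. **Internal consistency of the question.** The severity choice beneath it includes mild, which the question has just excluded. Some patients will resolve this by answering yes and marking mild; they are then told to call 911. Others will answer no and get no prompt. Two patients with the same symptom can thus be handled in opposite ways.
5. **Is the limit a general rule of the block?** No. The confusion question and the one on consciousness or alertness show no severity limit. The questions on weakness and speech are cut at the front by extraction, so nothing is inferred from them.
6. **Does another diary item supply the prompt?** The catch-all asks for symptoms "ot listed above". Dizziness is listed above, so a literal reader would pass over it. The questions on continuing symptoms and on illness, and the closing comments line, could hold the information, but none shows an instruction to call.
7. **Does something outside the diary supply it?** Adverse Reactions says subjects will be advised to contact staff and the treating physician immediately if a complication occurs. That has no severity threshold, but it leaves the patient to decide whether mild dizziness is a complication, after a form has implied that it is not. The 72-hour call and the visits ask about adverse events, but only when they fall due.

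The mismatch in steps 1 to 3 rests on legible words. The severity limit and the mild option both survive extraction.

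**The case against.** The strongest reply is that the diary is one of several routes. The patient can write mild dizziness in the comments, tick yes and mark it mild, raise it at the next contact, or act on the general advice about complications. The rule's list is also introduced as visual disturbances, so dizziness might be read as relevant only alongside an eye symptom. The first argument stands in part: it means no lost report can be demonstrated. It does not remove the mismatch, because none of those diary items carries a call prompt. The second is weak: the same list contains confusion, limb weakness and speech difficulty, and the diary asks about such symptoms separately from vision.

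Three stronger readings are tempting, and the documents do not support them.

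- **That a patient who loses vision has no fallback.** The second diary block sends her to the office immediately, or to a further contact outside business hours. This agrees with the reporting rule. No 911 step is legible there, and Adverse Reactions says that for blindness or any ophthalmic sign "the subjects must undergo immediate evaluation by a retinal specialist". But the block's closing line is redacted and garbled where a further step could stand, and the postoperative instructions are not shown. Absence cannot be concluded.
- **That the jaw-pain question, "in in Jaw at Rest", repeats the error.** It has the same limit, but pain after injection is expected, the vascular-occlusion guidance itself stresses unusual or worsening pain, and the diary's 0 to 10 scale records milder pain. A threshold for an urgent call is a defensible choice there.
- **That the delay can be bounded from the visit schedule.** After the first injection, the 72-hour call (day 3) is followed by visits in windows of days 11 to 17 and 25 to 31. This gives gaps of 11 − 3 = 8 to 17 − 3 = 14 days, then 25 − 17 = 8 to 31 − 11 = 20 days. These are not upper bounds. After a touch-up, Return Visits names only a 72-hour call and a 1-month visit, about 28 − 3 = 25 days apart, although the Protocol Summary can be read as restarting the 2-week visit. The figures also assume that the patient neither calls nor writes anything in the diary.

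**Conclusion.** The concern holds for the dizziness question alone. The form's threshold is narrower than the protocol's immediate-reporting rule, and the form contradicts itself by offering a grade that its own question excludes. A patient with mild dizziness who reads the form literally gets no prompt to call.

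It is at the low end of minor: one question on one form, 16 patients, other routes of capture, and no demonstrable lost event. The conclusion assumes that dizziness is a trigger in its own right and that the unseen postoperative instructions do not already ask for a call about mild dizziness. If they do, the practical gap closes, but the form should still be made consistent. The vision-loss instruction is an item to confirm, not a defect.

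**What to change.** Make two changes to the first diary block in the same edit.

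- Remove the severity limit from the dizziness question and keep the mild, moderate or severe choice.
- Split the closing instruction. For example: *If your only yes is mild dizziness, call the treating physician immediately. For moderate or severe dizziness, or a yes to any other question above, call 911.* Without this second change, every patient with mild dizziness would be sent to 911.

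Separately, check the unredacted closing line of the second block and the postoperative instructions. If neither already says so, add one sentence telling patients to call 911 or go to emergency care if they lose vision and cannot reach the physician at once. Leave the jaw-pain question as it is.

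The cost is the revision of one patient form and possibly one added sentence. Expect a few more mild events recorded and a few more calls among 16 patients. No analysis, sample size or visit changes.
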